**LIST OF ABBREVIATIONS**

GCP	Good Clinical Practice
CFR	Code of Federal Regulations
IRB	Institutional Review Board
DCTclock-pen	Original DCTclock test administered with a digitizing ball point pen and paper
DCTclock-tablet	A new version of the DCTclock test administered using a tablet and stylus
LAR	Legally Authorized Representative
MMSE	Mini-Mental State Exam
RBANS	Repeatable Battery for the Assessment of Neuropsychological Status
CDR-SOB	Clinical Dementia Rating Scale Sum of Boxes
AD	Alzheimer's Disease
PD	Parkinson's Disease
AE	Adverse Event
PI	Principal Investigator
FDA	Food and Drug Administration
SAE	Serious Adverse Event
UADE	Unanticipated Adverse Device Effect
CRF	Case Report Form
SOP	Standard Operating Procedures
ICF	Informed Consent Form
SRM	Study Reference Manuals
DSMB	Data Safety Monitoring Board
ITT	Intention To Treat
LoA	Limits of Agreement
ICC	Intraclass Correlation Coefficient
RMSD	Root Mean Squared Differences

MoCA	Montreal Cognitive Assessment
HIPAA	Health Insurance Portability and Accountability Act
MDR	Medical Device Reporting

**PROTOCOL SUMMARY**

**Title:** **A Randomized, Crossover Study to Assess the Reliability and Equivalence of Alternate Forms of the Digital Clock Drawing Test**

Randomized crossover trial consisting of two test visits separated by a washout period of 3 to 5 weeks. Subjects are randomized into two equal groups. Group 1 receives the digital pen (DCTclock-pen) version of the test at the first visit, with the tablet version (DCTclock-tablet) given at the second visit; Group 2 receives DCTclock-tablet at the first visit, followed by DCTclock-pen at the second visit. At Visit 1 (day 0), eligibility is assessed and a version of the DCTclock test is administered based on the group allocation. A battery of Linus Platform tests and reference standard tests are also administered. At visit 2 (day 21-35), eligibility is assessed and the alternate version of the DCTclock test is administered based on the group allocation. A battery of Linus Platform tests is also administered, together with reference standard tests. Equivalence of DCTclock-pen and DCTclock-tablet will be tested. Linus Platform test data will also be collected to develop novel measures of cognitive and motor function and assess their accuracy in detecting impairment, construct validity, and test-retest reliability. 200 subjects will be recruited to participate with the anticipation that 175 will be available for analysis.

The overall objectives of the study are to establish the equivalence of DCTclock-tablet to DCTclock-pen, to establish the safety of Linus Platform tests administered with a tablet or smartphone, and to collect data to enable the development and validation of Linus Platform tests.

**Objectives:**

Aim 1: Validate equivalence between DCTclock-pen and DCTclock-tablet for subjects with diverse levels of cognitive impairment

Aim 2: Characterize the safety profile of DCTclock-tablet and other Linus Platform tests

Aim 3: Obtain data to develop and validate Linus Platform tests

**Primary endpoint:**

- Equivalence of DCTclock-pen and DCTclock-tablet in assessing cognitive impairment.

**Exploratory endpoints:****Endpoint**

- Linus Platform tests individual and combined agreement with MMSE and RBANS assessment of cognitive status.
- Test-retest reliability of both individual Linus Platform tests and the combined Linus overall score compared to the test-retest reliability of the RBANS.

**Safety endpoints:**

- Incidence of serious device-related adverse events.

Population:	Healthy adults aged 55-95
Phase:	Pivotal
Number of Sites enrolling participants:	1-3
Description of Study Agent:	
DCTclock-tablet is an investigational device consisting of both hardware and software. Tablet hardware includes an Apple iPad and an Apple Pencil. An iPad application captures, encrypts, and transmits the encrypted data to Linus' secure servers. Tests are decrypted there, analyzed using a proprietary algorithm, and presented through a reporting portal in the same manner as the DCTclock-pen assessment.
 
Linus Platform tests also consist of both hardware and software. Hardware includes either an Apple iPad and Apple Pencil or a smartphone. Linus Platform tests include additional drawing-based tasks, decision making and reaction time assessments, mood and lifestyle questionnaires, speech and voice analysis, eye-tracking based memory tests, and gait and balance measurements.

Study Duration:	9-12 months
Participant Duration:	Up to 5 weeks

## SCHEMATIC OF STUDY DESIGN

1. Subject recruitment.
2. Those subjects who meet the inclusion criteria (men and women 55-95 years old) will be consented. Consent must be obtained from the subject or, if appropriate, their legally authorized representative (LAR) before any study procedures are completed.
3. Screening tests, a neurological assessment, one version of the DCTclock test, Linus Platform tests, and a standard neuropsychological test battery will be administered.
  - a. Screen for impairment of the dominant hand
  - b. Screen for drug/alcohol use
  - c. Mini-Mental State Exam (MMSE) (1). The MMSE will not be administered if a documented MMSE or Montreal Cognitive Assessment (MoCA) score  $\leq 18$  exists in the subject records and an LAR has consented to the study.
  - d. Hamilton-Veale Contrast Sensitivity (2)
  - e. Purdue Peg Board (3)
  - f. Brief neurological assessment
  - g. DCTclock-pen or DCTclock-tablet
  - h. Linus Platform drawing tasks with list learning

- i. Linus Platform decision making and reaction time tests (4)
- j. Linus Platform gait and balance assessment (5)
- k. Repeatable Battery for the Assessment of Neuropsychological Status (RBANS) (6)

4. After three to five weeks, screening tests, the alternate version of DCTclock, Linus Platform tests, and a standard neuropsychological test battery will be administered.

- a. Screen for impairment of dominant hand
- b. Screen for drug/alcohol use
- c. Alternate version of DCTclock from visit 1 (if DCTclock-tablet version was administered, then DCTclock-pen version is to be administered and vice versa)
- d. Linus Platform drawing tasks with list learning
- e. Linus Platform decision making and reaction time tests with PHQ-9 mood assessment
- f. Linus Platform lifestyle questionnaire (7)
- g. Linus Platform speech elicitation tasks (8)
- h. Linus Platform eye tracking-based memory assessments (9)
- i. Linus Platform gait and balance assessments
- j. RBANS
- k. Linus Platform reaction time test

## 2 INTRODUCTION: BACKGROUND INFORMATION AND SCIENTIFIC RATIONALE

### 2.1 BACKGROUND INFORMATION

Cognitive impairment, specifically dementia and Alzheimer's Disease, is one of the largest health problems in the United States. There are 6 million individuals in the U.S. with some form of dementia, representing an annual cost to the healthcare system of \$225 billion. 5.3 million of these people have Alzheimer's Disease, the 6th leading cause of death in the U.S. By 2050, these numbers are expected to triple to nearly 16 million Americans diagnosed with dementia, with an annual cost of more than \$1 trillion (10) . Current standard of care to address this enormous health problem is lengthy for both practitioners and patients, potentially invasive, expensive, and cannot detect impairment early enough to intervene and potentially change the course of disease. There is an enormous market need for a cost effective, reliable, objective, noninvasive, accurate, way to identify cognitive impairment at its earliest stages.

#### DCTclock™

DCTclock™ is a neuropsychological test based on the traditional Clock Drawing Test that may provide a more sensitive measure of cognitive state (11). The DCTclock test, offered by Linus Health, capitalizes on the clever design of the traditional Clock Drawing Test but uses patented advanced analytics and technology to evaluate both the final drawing and the process that created it, producing a more robust assessment. The DCTclock test, is cleared to market and uses a digitizing ballpoint pen that, while drawing, also digitally records its position on the paper 75 times a second with a spatial resolution of two one-thousandths of an inch. DCTclock software detects and measures changes in pen position that cannot be seen by the naked eye, and because the data is time-stamped, the system captures the entire sequence of behaviors (e.g., every stroke, pause or hesitation), rather than just the final result. This enables the capture and analysis of very subtle behaviors that have been found to correlate with changes in cognitive function. These measurements are all operationally defined in code (hence free of user bias) and carried out in real time. To distinguish this version of the product, it will be referred to as DCTclock-pen. DCTclock-pen hardware includes the digitizing pen, pen dock, and printed test form. As a participant draws, the pen captures and encrypts the test data.

While DCTclock-pen is an easy-to-use and accurate cognitive test, enabling its administration using a tablet (DCTclock-tablet) will ease deployment by leveraging equipment more commonly found in clinical settings and that require less maintenance, with a concomitant decrease of cost and administrator burden. Hardware for DCTclock-tablet includes an Apple iPad and an Apple Pencil. Like the digital pen, the iPad captures and encrypts data as the participant draws with the Apple Pencil. In both cases – pen and tablet - the data from the DCTclock test is securely transmitted to Linus's HIPAA compliant servers where it is decrypted, then analyzed using advanced analytics including proprietary state-of-the-art artificial intelligence and machine learning techniques. Following test analysis, a report is instantly generated and immediately available for review by the investigator via a secure website. In addition to facilitating deployment by eliminating the need for unique hardware (the digitizing ballpoint pen), transitioning DCTclock to a tablet can also enable harmonization with other tablet-based cognitive assessment platforms such as the NIH Toolbox and tests under development in the Linus Platform.

The primary endpoint of this study is to determine the equivalence of DCTclock-pen and DCTclock-tablet in assessing cognitive impairment.

#### Linus Platform Tests

'Linus' is a multimodal, remote brain health monitoring platform designed to integrate scientifically validated, best-in-class technologies into a single 'plug-and-play' solution for longitudinal, in situ data collection. The platform brings together, into one mobile application, end-point solutions that rely mainly on smartphone or tablet sensors to collect various measures of patients' cognitive and motor functions. Linus Platform Tests will be included in this study to gather preliminary data. Ultimately, a battery of tests including DCTclock and others in the Linus Platform could be used clinically for a more accurate assessment of cognitive function, but it is first essential to determine how these tests correlate and complement each other by administering them in parallel in a defined cohort. An additional aim of this protocol is to obtain data to develop and validate tests on the Linus Platform. Linus Platform tests are at various stages of development and validation and include:

- Drawing-based tasks
- Measures of decision making and reaction time (4)
- Speech elicitation tasks (8)
- Eye tracking-based memory assessments (9)
- Gait and balance assessments (5)
- Lifestyle questionnaire

## 2.2 RATIONALE

The overall objectives of the study are to establish the equivalence of DCTclock-tablet to DCTclock-pen, to establish the safety of DCTclock-tablet and Linus Platform tests administered with a tablet or smartphone, and to collect data to enable the development and validation of Linus Platform tests.

## 2.3 POTENTIAL RISKS AND BENEFITS

### 2.3.1 KNOWN POTENTIAL RISKS

#### DCTclock

DCTclock-pen is a class II, 510(k) exempt medical device and has been used in research and clinical settings with no reported adverse events. DCTclock's validation study (11) had the following safety outcome:

435 participants took a total of 841 DCTclock tests during the DCT032 study. A total of 37 adverse events (AE) were recorded in this population. The percentage of participants experiencing an AE during the study window (1-4 weeks) is not unexpected given that the study included an older population aged 55 to 95 years old. Of the total 37 AEs, only 1 was a serious adverse event (SAE). The SAE was reviewed by the study medical monitor and found to be unrelated to the protocol or study device. There were no reported unanticipated adverse device effects and no reported serious device related AEs.

The 36 non-serious AEs were reviewed by the study Adverse Event Review Team and found to be unrelated to the study device. The most frequent AEs reported were colds and gastrointestinal upset and both occurred in less than 1 percent of participants (4 in 435).

DCTclock-tablet differs from DCTclock-pen predominantly in the use of an Apple iPad and Apple Pencil instead of the digitizing ballpoint pen and paper. It is reasonable to assume that the risk level for DCTclock-tablet will be minimal and the risk profile will be similar to that seen with DCTclock-pen.

#### Linus Platform Tests

- Additional drawing-based tasks where subjects draw on an iPad with an Apple pencil. Risks associated with this task are minimal and include fatigue and loss of confidentiality.
- A measure of decision making & reaction time where subjects tap the screen of a tablet in response to visual prompts. Risks associated with this task are minimal and include fatigue and loss of confidentiality.
- A speech elicitation task where subjects provide audio feedback such as describing a picture, recalling a story, reading sentences, and recalling lists of words using a tablet. Risks associated with this task are minimal and include fatigue and loss of confidentiality. This assessment includes voice recordings, but the recordings will not be associated with subject identifiers. This assessment requires subjects to remove any facial coverings for the duration of the task (~10 minutes).
- An eye tracking based memory assessment where subjects view images on a tablet screen. Images are later shown again with minor modifications and a video recording is used to determine the length of time the subject looks at each area of the screen. Risks associated with this task are minimal and include fatigue and loss of confidentiality. This assessment includes full face video recordings, but the recordings will not be associated with subject identifiers. This assessment requires subjects to remove any facial coverings for the duration of the task (~5 minutes).
- A gait and balance assessment where subjects complete short walking and standing tasks either with or without additional cognitive load (serial subtraction) while carrying a smartphone. The physical requirements are limited to standing with eyes open or closed for 30 seconds at a time (up to 2 min total) and walking at a comfortable pace for less than 2 minutes total. Although unlikely, the potential risks of these physical tasks include fatigue, sprains, muscle soreness and falling.
- A Lifestyle questionnaire where the subject responds to yes or no questions about their lifestyle on a tablet. Risks associated with this task are minimal and include fatigue and loss of confidentiality.

### Overall Study Risks

- Cognitive testing can result in general fatigue, but participants will be allowed breaks between tests, as necessary, to alleviate any fatigue.
- Some minimal physical tasks are required for this study. Should a participant become uncomfortable completing the standing and walking tasks due to physical challenges or fatigue, they will be instructed to stop the task immediately.
- Should a participant express any concern with their performance on cognitive tests, they will be directed to discuss those concerns with their Primary Care Physician. No results from the testing conducted in this protocol will be shared with participants or used to guide their clinical care.
- Federal and local guidelines as well as site specific policies will be followed to minimize exposure of research subjects to COVID-19 in line with current clinical care.
- While there is always a risk of loss of confidentiality of study data, all data will be stored securely at the sites and de-identified prior to transfer to the sponsor or their partners.

Cognitive tests can only be validated through use on human subjects. As the risks associated with this study are minimal, the benefit of validation of sensitive assessments of cognitive state outweighs the potential risks.

---

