#### **Linus Platform decision making and reaction time tests (4)**

Participants will be asked to complete three short cognitive tasks presented on a tablet supplied by the study. These tasks are sourced from DANA Brain Vital (Anthrotronix, Inc.), which is an FDA-cleared, modular application that measures cognitive efficiency by tracking subtle changes in cognitive capabilities. DANA assessments are highly sensitive and designed for high-frequency use and focus on accuracy and reaction time—two key elements of cognitive efficiency. Each task takes 1-2 minutes to complete. Subjects will also be asked to complete the PHQ-9 depression screening tool (13). An iPad application captures, encrypts, and transmits the encrypted data to Linus' HIPAA compliant servers.

The tasks included are as follows:

Task	Description
Simple Reaction Time	A bullseye stimulus appears on the screen, and the test taker taps it as quickly as possible
Procedural Reaction Time	A number (1, 2, 3 or 4) appears on the screen, and the test taker must indicate which number was displayed by tapping either the “1 or 2” button or the “3 or 4” button
Go/No-go	A building with six windows is displayed, and either a “friend” (green) or “foe” (gray) alien will appear in a window. The test taker must tap the “BLAST” button only when foe stimuli appear
PHQ-9	Self-reported depression screening tool

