### **Linus Platform lifestyle questionnaire**

Adapted from the Barcelona Brain Health Initiative (7), this questionnaire includes up to 57 yes/no questions about the participant's lifestyle that are associated with cognitive performance. These questions are presented on a tablet and the subject uses their finger to select yes or no for each question.

Participants who take part in this study will also receive standard, accepted neuropsychological tests including RBANS (6) and MMSE (1) in addition to DCTclock and the Linus Platform tests.

All tests administered in this study are non-invasive and do not introduce energy into the subject. Study test results are not reported to participants or used to guide their clinical care. Additional information about the DCTclock-tablet and Linus Platform tests can be found in the Investigator's Brochure.

---

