#### 7.1.1 STUDY SPECIFIC PROCEDURES

- Demographics and review of medical history and current medications
- Assessment of impairment of the dominant hand
- Assessment of recreational drug or alcohol use
- MMSE
- Hamilton-Veale Contrast Sensitivity
- Purdue Peg Board
- Brief neurological assessment
- DCTclock-pen
- DCTclock-tablet
- Linus Platform tests
  - Drawing-based tasks
  - Decision making & reaction time tasks
  - Mood assessment (PHQ-9)
  - Lifestyle questionnaire
  - Speech elicitation tasks

- o Eye tracking-based memory assessments
- o Gait and balance assessments
- RBANS

No results from these assessments will be provided to the participant or used to guide their clinical care.

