### 7.3.2 VISIT 2 (FINAL STUDY VISIT)

#### Visit 2 (Day 21-35) ~ 94 minutes total

Visit 2 Screening (2 mins)	Time Estimate
Assessment of impairment of the dominant hand	1 min

Assessment of recreational drug or alcohol use/change in medications	1 min
--	-------

If a subject screen fails at any step, they will not complete the remaining assessments; eligible subjects will complete the following study assessments.

Visit 2 Study Assessments (92 mins)	Time Estimate
Alternate version of DCTclock from visit 1 (if DCTclock-pen version was administered, then DCTclock-tablet version is to be administered and vice versa based on randomization group allocation)	5 mins
Linus Platform drawing tests with list learning	15 mins
Linus Platform decision making and reaction time assessments with PHQ-9	10 min
Linus Platform lifestyle questionnaire	10 min
Linus Platform speech elicitation tasks	10 min
Linus Platform eye tracking-based memory assessment	5 mins
Linus Platform gait and balance assessment	5 mins
RBANS	30 min
Linus Platform reaction time assessment	2 mins

This visit ends the participant's participation in this study.

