## 7.3.4 SCHEDULE OF EVENTS TABLE

Procedure	Screening/Visit 1	Visit 2
Time	Day 0	Within 3-5 weeks of visit 1
Consent	X	
Inclusion/Exclusion Criteria	X	X
Medical History/Demographics	X	
MMSE	X*	
Hamilton-Veale Contrast Sensitivity	X	
Purdue Peg Board	X	
Brief Neurological Assessment	X	
DCTclock Test (either digital pen or tablet version)	X	X
Linus Platform drawing tests	X	X
Linus Platform decision making and reaction time assessments	X	X^ &
Linus Platform lifestyle questionnaire		X
Linus Platform gait and balance assessment	X	X
RBANS	X	X
Linus Platform speech elicitation assessments	X#	X
Linus Platform eye tracking-based memory assessments		X
Assessment of adverse device effects	X	X

\*- MMSE not administered if a LAR consents to the study due to a documented prior MMSE or MoCA score of  $\leq 18$

 PHQ-9 depression screen is included in the decision making and reaction time assessments on visit 2 only

^ reaction time only is assessed twice on visit 2

#- List learning only is combined with the drawing tests on visit 1. All speech and voice assessments are given on visit 2.

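### The PHQ-9 depression screen is given only at the last visit, is covered by the bar on using results in care, and no visible step has site staff read the answers

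*Protocol*

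**What the plan says.** Protocol 6.1, on the decision making and reaction time tests, introduces the instrument: "Subjects will also be asked to complete the PHQ-9 depression screening tool". The footnote to the schedule in 7.3.4 fixes the timing: "PHQ-9 depression screen is included in the decision making and reaction time assessments on visit 2 only". Section 7.3.2 closes the Visit 2 table with: "This visit ends the participant's participation in this study".

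The rule on results appears three times.

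- **7.1.1**, directly below a procedure list that includes the PHQ-9 as the mood assessment: "No results from these assessments will be provided to the participant or used to guide their clinical care".
- **6.1**, under the lifestyle questionnaire: "Study test results are not reported to participants or used to guide their clinical care".
- **2.3.1**, Overall Study Risks: "No results from the testing conducted in this protocol will be shared with participants or used to guide their clinical care".

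The only referral route tied to testing is also in 2.3.1. It opens with "Should a participant express any concern with their performance on cognitive tests" and sends that participant to their Primary Care Physician.

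On data flow, 13.4 says that PHQ-9 responses are held encrypted on the tablet, transmitted directly to the sponsor's servers, and then deleted from the device.

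**The concern.** A depression screen differs from the other tests in this battery. Withholding scores from tablet tests still under development is sensible. The PHQ-9, however, is described in the protocol itself as a screening tool and is cited to a published source. A positive answer may call for someone to act, and here it arises at the final contact under a rule that forbids passing it on or using it in care.

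Two things are at stake. A participant with a positive but non-urgent screen could leave with nothing done, and staff who follow the protocol would be right to do nothing. Staff might also never learn of an answer that did need prompt attention, because nothing visible tells them to look. The study recruits partly from neurology clinics (5.3) and admits people with an MMSE or MoCA of 18 or less when a legally authorized representative (LAR) consents (5.2, 13.3.2). Relying on participants to raise the matter themselves is a weak safeguard in that group.

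**Working it through.** The plan gives no statistical figure on this point, so the check is mainly a reading of the text, with simple counts.

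**Is the PHQ-9 given only at Visit 2?** Yes. The Visit 1 table in 7.3.1 omits it. The study schematic, 7.3.2, 7.3.4 and SAP 10.1 all place it at Visit 2. The SAP Appendix A shells leave Visit 1 cells open for it and list it under test-retest. That is a separate inconsistency in the shells and does not change the schedule.

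**Does the rule cover it?** The 2.3.1 statement sits in a bullet about worry over cognitive performance, so read alone it could be limited to cognitive tests. The 7.1.1 statement cannot be read that way, because its list names the PHQ-9. Statements of the rule: 3. Exceptions for the PHQ-9: 0.

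**Must anyone at the site read the answers?** Steps found that require this before the participant leaves: 0. The nearest texts are these.

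| Text | What it provides | Why it is not a review step |
|---|---|---|
| 2.1 | Immediate report to the investigator | Described for DCTclock only |
| 6.1.2 | Platform shows results to the administrator | General feature; the PHQ-9 is not named and no reading is required |
| 2.3.1 | "all data will be stored securely at the sites and de-identified prior to transfer to the sponsor or their partners" | Suggests site access, but 13.4, which is specific to the PHQ-9, describes only tablet, sponsor server and deletion |
| 14.1 | Incoming data reviewed for adverse events | No reviewer or timing is named |
| 8.3, 8.4 | Adverse event (AE) inquiry at each visit; follow-up to resolution or stability | Depends on what is reported; a condition present at screening is baseline unless it worsens |
| 8.2.2, SAP 10.1 | Doubtful observations are reported as AEs; the AE table has a PHQ-9/lifestyle relationship category | Attributes an event once known; does not prompt anyone to read the answers |
| 7.3.1, SAP Appendix A | Visit 1 history, including anxiety or depression | Records what is already known |

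**How many people?** The Protocol Summary recruits 200 and expects 175 to be available for analysis. Taking 175 as the number completing Visit 2, the rule covers about 175 PHQ-9 forms.

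**Workload of reading them.** Accrual is 22 a month (5.3).

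- All sites: 22 × 175/200 = 19.25, about 19 forms a month. Check: 175 / 9 months = 19.4.
- Per site, with the two sites in the SAP document history: 19.25 / 2 = 9.6, about 10 a month.

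**Is there time at the visit?** The Visit 2 assessments total 5 + 15 + 10 + 10 + 10 + 5 + 5 + 30 + 2 = 92 minutes, which matches 7.3.2. The module with the PHQ-9 ends at 5 + 15 + 10 = 30 minutes, leaving 92 − 30 = 62 minutes if the listed order is kept. No text makes that order binding.

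**The case against.** The strongest reply is that the protocol is less rigid than the rule suggests. Section 14.3 waives prior sponsor approval for a deviation made to protect life or physical well-being in an emergency. A reader might infer that staff are forbidden to respond even to an urgent answer; 14.3 does not support that reading. It stands as an answer for emergencies that staff know about. It does not help them find out, and it does not reach a positive screen that is not an emergency. The investigator's power in 5.4.1 to act on a medical condition extends only to ending participation, which at Visit 2 is ending anyway.

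A second reply is that a review step would normally sit in operational documents. The Investigator's Brochure (6.1.5), Study Reference Manual (7.1), AE/SAE Handling Plan (8.5), consent form and site policies were not available. A reader might infer that no one ever looks at the answers; the visible text does not establish that. But if such a step exists, referring a non-emergency participant on the strength of it would still run against 7.1.1.

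Third, the harm is not quantified. That is correct: the documents give neither a positive rate nor a cut-off, so nothing can be said about how many participants would be affected.

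Fourth, a uniform no-results rule is a legitimate choice in a study that offers no direct benefit (2.3.2). That holds for the other tests. It is less persuasive for an instrument that the protocol itself describes as a screen.

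**Conclusion.** The point holds as a gap in participant protection. The PHQ-9 is collected at the last contact, the rule in 7.1.1 bars telling the participant or using the result in care, and no visible step requires the site to read the answers. The gap is mainly the non-emergency positive screen, together with the lack of anything that would bring an urgent one to light.

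It covers about 175 expected participants, each screened once; the number who would screen positive is unknown. The conclusion assumes that the unseen documents do not override the protocol text. A review step in them would narrow the gap but leave the conflict over acting on the result. Confidence is medium for that reason.

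A reader might also infer a threat to the trial's conclusions. There is none: the PHQ-9 appears only among the exploratory measures (SAP 3.2.3), and the equivalence analysis, its power and the safety endpoint do not depend on it.

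**What to change.** This is a cheap improvement. In 7.1.1, and to match in 6.1 and 2.3.1, add after the rule: *The PHQ-9 is excepted: trained site staff read the responses before the participant leaves Visit 2, and the investigator directs a participant with a positive screen (and the LAR, where one consented) to their Primary Care Physician or follows site policy.*

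In addition:

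- Set the threshold for a positive screen in the Study Reference Manual.
- Amend 13.4 so that the site can see the answers at the visit, on screen or on a paper form.
- Hold non-urgent conversations until testing ends, so that no later test score is affected.
- Align the consent wording, and leave the rule unchanged for every other test.

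The cost is setting up the view, since 13.4 now routes answers away from the site, and reading about 19 forms a month in total, or about 10 per site at two sites. Someone among the existing staff must be qualified to handle a positive. Participants may answer less candidly if they know the form is read, which would touch only an exploratory measure. Sending someone to their own physician makes no diagnosis, so it does not appear to disturb the device exemption condition in section 17.
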